# **PROTOCOL SYNOPSIS FOR ROB0037**

TITI F	
TITLE	STRUCTURE AND FUNCTION MRI OF ASTHMA
SPONSOR	Robarts Research Institute
	Western University
DDO IECT DUASE	[name]
PROJECT PHASE	Exploratory Study
INDICATION	Asthma
OBJECTIVE	
 
Acquire Xe MRI and optimize analysis methods to generate in vivo measurements
 

	• Evaluate  Xe MRI measurements over time and in response to therapy, relate them to airflow, dyspnea, airway remodeling and inflammation and validate using x-ray computed tomography (CT) and histology
	
 
Evaluate image analysis methods that generate 129Xe MRI temporal lung function maps as image guidance/therapy planning tools for targeted asthma therapy
 

	
 
Develop Xe MRI structure-function models computationally to understand mechanisms of localized therapy response
 

	
 
Evaluate oscillometry outcomes of the respiratory system as they correlate to lung function abnormalities detected using Xe MRI
 

	• For the subset of patients identified as underperceivers using asthma control and quality of life questionnaires, we will acquire fMRI to determine if severe asthmatics with poor control exhibit baseline differences in brain structure and function compared to healthy volunteers, and if these alterations influence asthma symptom perception
	
 
To determine if differences in brain structure and function are related to lung function abnormalities quantified by pulmonary MRI
 

	
 
In healthy volunteers and the subset of asthmatic participants identified as underperceivers, to determine if differences exist in resting state brain connectivity pre- and post-Methacholine challenge
 

	
 
In the subset of asthmatic participants, to evaluate the differences in resting state brain connectivity compared to healthy volunteers post-Methacholine Challenge
 

STUDY DESIGN	Longitudinal Study
PLANNED TOTAL SAMPLE SIZE	200 Asthmatic participants & 30 Healthy Volunteers

DATE: November 15, 2024

PARTICIPANT	SELECTION	Males and females, ages 18-85 years old that are either				
CRITERIA		healthy volunteers or have a clinical diagnosis of				
		Asthma.				
TREATMENTS/MOD	DALITY	MRI, fMRI, MDCT, spirometry, plethysmography, DLco, FOT, MBNW, FeNO, Borg Dyspnea Scale, MRC Dyspnea Scale, Quality of Life Questionnaires, Asthma Control Questionnaires, and St. George's Respiratory				
		Questionnaire.				
DOSAGES		There is no study medication evaluated. As part of the lung MRI, participants will inhale polarized  Xe and/or  He at a dosage of 5 ml/kg body weight diluted with helium-4 (  He) gas to 1.0L. The polarized  Xe/  He mixture will be inhaled in a single breath-hold. This is intended to fill the lungs with the gas, allowing for complete imaging. Participants will inhale the gas mixture up to five times at each imaging session.				
ROUTE OF ADMINI	STRATION	Oral inhalation directly into lungs from a Tedlar ® plastic bag with an attached breathing tube/straw containing a stopcock on-off valve while inside MR magnet bore.				
MAIN PARAMETER -SAFETY	S OF:	Heart rate and oxygen saturation will be monitored throughout the imaging session and recorded. Adverse events will be recorded.				
-EFFICACY		
 
129Xe MRI ventilation image analysis (VDP)
 
129Xe MRI diffusion-weighted image analysis (ADC)
 
129Xe MRI dissolved phase spectroscopy analysis
 
Pulmonary Function Testing
 
MDCT image analysis
 
				
DURATION OF STU	IDY	Q1 2013 - Q4 2028				

# **PROTOCOL SYNOPSIS FOR ROB0037**

# **MAGNETIC RESONANCE IMAGING (MRI) PROCEDURE:**

Participants will be screened for contraindications by the Study Coordinator and MR technologist. Prior to being made comfortable on the scanner bed in the magnet, participants will be asked to perform a 16-second breath-hold test using a dose bag containing medical grade nitrogen (N2) with an identical volume to that used for xenon-129 (129Xe). This maneuver ascertains their ability at that time to undergo administration of 129Xe and/or 3He gas and a 16-second breath-hold for the MR study. They will be placed in the 3T MR scanner with one of three 129Xe chest coils fitted over their torso and chest. Hearing protection will be provided to each participant to muffle the noise produced by the gradient RF coils. A pulse oximeter lead will be placed on the participant's finger to monitor heart rate and oxygen saturation. MRI will be performed for up to a period of 30 minutes. All imaging will be performed in a "breath-hold" fashion. All participants will have supplemental oxygen provided via nasal cannula at a flow-rate of 2 liters per minute during the scanning process. There will be four breath-holds involving the hyperpolarized gases.

Protocol ROB0037, Robarts Research Institute

Version 16

DATE: November 15, 2024

Up to four different types of pulmonary images will be acquired in the coronal plane during the single visit: 1) proton (H) thoracic cavity, 2) Xe and/or He static ventilation, 3) Xe and/or He diffusion-weighted, and 4) Xe dissolved phase. Heart rate and oxygen saturation will be monitored throughout the imaging session.

For healthy volunteers and the subset of asthmatics who have been identified as underperceivers of dyspnea and exhibiting poor disease control using asthma control and quality of life questionnaires, resting state functional MRI (RS-fMRI) will also be performed pre- and post-methacholine challenge on the first visit only. Participants will be placed in the 3T MR scanner with a specialized coil fitted around their head. Hearing protection will be provided to each participant to muffle the noise produced by the gradient RF coils. A pulse oximeter lead will be placed on the participant's finger to monitor heart rate and oxygen saturation. MRI will be performed for up to a period of 20 minutes. All participants will have supplemental oxygen provided via nasal cannula at a flow-rate of 2 liters per minute during the scanning process. Participants will be placed in the supine position and will be asked to remain motionless during the scanning process. The scanning process will involve the acquisition of various images: an anatomical image, a blood oxygenation level dependent (BOLD) contrast image, and a diffusion tensor image (DTI). These images will provide information about neural activation and anatomical connections between brain areas. Brain fMRI and lung MRI using Xe will be performed within five minutes of each other, and the order in which they are performed will be randomized for each participant.

Logs and records of gas exposure will be maintained for every volunteer in this study. Adverse events and pulse oximetry measurements during MRI will be recorded. If oxygen saturation falls to <80% continuously for ≥15 seconds, scanning will be discontinued, and the patient will be provided supplemental oxygen as necessary until oxygen saturation recovers to the patient's baseline value. This patient will then be discontinued from the study. Oxygen desaturation below 88% during any breath hold will be considered an adverse event.

#### **PULMONARY FUNCTION TESTING**

Full pulmonary function tests including spirometry, lung volumes and diffusing capacity of carbon monoxide (DLco) will be performed according to American Thoracic Society (ATS) guidelines using MedGraphics Elite Series, MedGraphics Corporation. St. Paul, MN USA and/or nDD EasyOne Spirometer, nDD Medical Technologies Inc. Andover, MA USA. All measurements will be performed in the Pulmonary Function Laboratory at Robarts Research Institute. Lung clearance index (LCI) will be derived from the multiple breath nitrogen washout (MBNW) test. Participants breathe normally into a mouthpiece connected to a device, the NDD Easy-One Pro Lab, for approximately 3-5 minutes. Fractional exhaled nitric oxide (FeNO) will be measured using the NIOX VERO® (Circassia Pharmaceuticals Inc., Morrisville, NC, USA).

# FORCED OSCILLATION TECHNIQUE (FOT)

FOT will be performed at each visit using the tremoFlo™ airway oscillometry system (THORASYS Thoracic Medical Systems, Montreal, QC). FOT measures the mechanics of the respiratory system and is a method of evaluating lung function without patient effort, by superimposing a gentle multi-frequency airwave onto the patient's respiratory airflow. Patients breathe normally throughout the measurement sequence via a disposable mouthpiece. Measurements will be performed in the Pulmonary Function Laboratory at Robarts Research Institute and according to the recommended guidelines set by the

DATE: November 15, 2024

European Respiratory Society (ERS) (Oostveen et al., Eur Respir J 2003; 22: 1026–1041).

#### **METHACHOLINE CHALLENGE**

Methacholine Challenge and Salbutamol rescue: Methacholine Challenge will be performed in the Robarts Pulmonary Function Laboratory at Visit 1. According to the ATS guidelines (after recording baseline forced expiratory volume in 1 second (FEV1)) up to and including the concentration of Methacholine required to decrease FEV1 20% from baseline (PC20).

#### SPUTUM INDUCTION

Induced sputum will be collected at Visit 1, 1c and optional annual in-person visits. Sputum induction is a relatively non-invasive method to obtain sputum for cell or fluid phase inflammatory indices, culture or cytology. It is performed with an aerosol of normal or hypertonic saline generated by an ultrasonic nebulizer. Samples will be analysed by study staff at Robarts Research Institute. Analysis will begin within 2 hours of sputum collection, and samples will be kept in the locked sputum lab until analysis is complete, at which time samples will be destroyed.

# MULTI-DETECTOR ROW COMPUTED TOMOGRAPHY (MDCT)

Thoracic low dose MDCT will be performed with the same inhalational breath-hold volume and maneuver (nitrogen ( $N_2$ ) gas only) used for MRI. CT imaging will be performed using either an Aquilion ONE CT scanner (Canon Medical Systems USA, INC., Tustin, CA, USA) or a Lightspeed VCT CT scanner (General Electric, Waukesha WI, USA) at either Robarts Research Institute in London, Ontario or at University Hospital, located next door to Robarts Research Institute. Participants will be scanned in the supine position and during inspiration breath-hold from functional residual capacity (FRC) after inhaling 1L of  $N_2$  gas as previously described in order to match CT and MRI breath-hold volumes and anatomy.

#### **QUESTIONNAIRES**

Participants with asthma will complete the Asthma Quality of Life Questionnaire with Standardised Activities (AQLQ(S)) (bi-weekly), and Asthma Control diary (weekly), and will upload to our website monthly using a confidential and password protected upload. The AQLQ(S) was developed to measure the functional problems (physical, emotional, social and occupational) that are most troublesome to adults (17-70 years) with asthma. Respiratory related quality of life will be assessed using the SGRQ. (Jones, P. W., et al. 1992) This tool is used to measure health-related quality of life.

The Modified Borg Dyspnea Scale and MRC Dyspnea scale will evaluate breathlessness at each clinic visit.

#### ANALYSIS:

We will measure hyperpolarized noble gas MRI gas distribution after breath-hold using the ventilation defect percent (VDP), Xe and/or He MRI measurements of gas trapping apparent diffusion coefficient (ADC) and Xe MRI dissolved phase spectroscopy measurements of pulmonary gas exchange. FOT measures of respiratory system resistance (Rrs) and reactance (Xrs) will be acquired following the experimental methods and recommended reporting set by the ERS. For the subset of patients performing resting state fMRI, BOLD contrast will be used to measure physiological changes in blood flow

Protocol ROB0037, Robarts Research Institute Version 16

DATE: November 15, 2024

and oxygen metabolism in the brain. The magnetic properties of oxygen-rich and oxygen-deficient blood provide a MR signal to indicate underlying neural activity changes. We will also acquire DTI from participants undergoing fMRI. DTI tracks the random motion of water in neural fibers to provide information about the orientation, magnitude, and direction of neural connections.

#### **DURATION OF THE STUDY:**

Study duration for each participant is up to 10 years (up to 10 face-to-face visits, 2 phone calls). A sub-set will also visit at 7  $\pm 2$  days and 14  $\pm 2$  days to evaluate reproducibility and for generation of temporal spatial maps. Each participant will spend approximately 1 ½ to 2 hours on site for each visit, including screening, full pulmonary function tests and MRI. There is a 24-hour follow up for adverse events after the end of the final visit.

# **GLOSSARY OF ABBREVIATIONS**

H Proton
 He Helium-3
 He Helium-4
 Xe Xenon-129

ACQ Asthma Control Questionnaire
ADC Apparent Diffusion Coefficient

**AE** Adverse Event

**AQLQ(S)** Asthma Quality of Life Questionnaire

ATS American Thoracic Society

CI Confidence IntervalCV Coefficient of Variation

**DLCO** Diffusing Capacity of Lung for Carbon Monoxide

DS Defect Score
DV Defect Volume

**ERS** European Respiratory Society **FeNO** Fractional Exhaled Nitric Oxide

**FEV**1 Forced Expiratory Volume in one second

FOT Forced Oscillation Technique FRC Functional Residual Capacity

FVC Forced Vital Capacity
IC Inspiratory Capacity

**MDCT** Multi-Detector Row Computed Tomography

MRC Medical Research Council

MRI Magnetic Resonance Imaging

N2 Nitrogen

RS-fMRI Resting State Functional Magnetic Resonance Imaging

PFT Pulmonary Function Test

**PVV** Percentage Ventilation Volume

RBC Red Blood Cell

**Rrs** Respiratory System Resistance

**SAE** Serious Adverse Event

**SGRQ** St. George's Respiratory Questionnaire

SV Slow Vital Capacity

# Protocol ROB0037, Robarts Research Institute

Version 16

DATE: November 15, 2024

TCV	Thoracic Cavity Volume
TGV	Thoracic Gas Volume
TLC	Total Lung Capacity
VDP	Ventilation Defect Percent
VDV	Ventilation Defect Volume

Xrs Respiratory System Reactance

DATE: November 15, 2024

#### **PART I: STUDY DESIGN AND CONDUCT**

#### 1. BACKGROUND AND RATIONALE

Asthma is commonly diagnosed and characterized using the forced expiratory volume in 1s (FEV1) - a simple and inexpensive spirometry measurement of airflow obstruction. As a result, current and newly developed asthma therapies are mainly directed towards improvements in FEV1. Unfortunately, FEV1 measurements do not always capture peripheral airway dysfunction or provide information relevant to the heterogeneity of airway dysfunction, which in asthma may have profound consequences for the work of breathing and gas exchange. We also now realize that the specific airway abnormalities that may be directly responsible for asthma symptoms and exacerbations are most likely heterogeneously distributed in the lung [1] and this information cannot be easily evaluated using global airflow measurements. Because of this, we think that methods for measuring and mapping regional asthma structure-function are necessary before we can achieve the critical breakthroughs required for the development of new asthma therapies.

Despite decades of active research and the staggering and growing societal burden of asthma, current clinical tools cannot provide a non-invasive way to: 1) differentiate between diseased and normal airways in individual asthma participants, 2) identify regional structural and functional targets for asthma therapy, and, 3) measure regional asthma changes over time or in response to therapy. In other words, there is no way to measure regional lung abnormalities in asthma, making it difficult if not impossible to develop and test regional asthma therapies. We think that airway remodeling is mainly masked by global function measures and has real clinical impact on asthma symptoms, control and quality of life.

Hyperpolarized noble gas magnetic resonance imaging (MRI) of the lung is a relatively new imaging method that allows depiction of both lung function and morphology [2-7]. Hyperpolarized gases are a new class of MR contrast agent that, when inhaled, provide high temporal and spatial resolution MR images of the lung airspaces. Since no ionizing radiation is involved, hyperpolarized gas MR imaging is ideal for the evaluation of lung diseases. With hyperpolarized gases, the nuclear spins of the gas atoms are brought into alignment outside of the MR scanner via a process called optical pumping, yielding high polarizations and permitting the visualization of the lung airspaces with MR imaging despite the low physical density of the gas in the lung. Two non-radioactive, or stable isotopes of noble gases, helium-3 (He) and xenon-129 (Xe), can be hyperpolarized. Until recently, higher polarizations could be achieved with He than with Xe, so in humans, He was more commonly used for hyperpolarized gas MR imaging of the lungs [8-13]. Recently, the technology has been developed to provide large quantities of highly polarized Xe [14].

Several applications of noble gas MRI are in the process of development. Such techniques include diffusion-weighted and relaxation-weighted imaging. These techniques take advantage of the fact that the rate of loss of polarization is significantly influenced by the local concentration of molecular oxygen and the fact that the gas diffusion is governed by small airway space volumes. These data can be used to create maps of the lung reflecting regional ventilation/perfusion and micro-airway sizes [15]. Other data that can be obtained with noble gas MRI includes the volumes of ventilated and unventilated lungs that can then be analyzed to determine the homogeneity of gas distribution within the airspaces [16,17].

Furthermore, accurate perception of asthma symptoms is essential for motivating appropriate health management behavior, such as seeking timely medical and self-

DATE: November 15, 2024

treatment. "Underperceivers" are classified as asthmatics who do not experience the sensation of dyspnea during asthma flair ups [18,19]. Inaccurate symptom perception is a contributing factor to increased morbidity and mortality in asthma patients [18]. The blunted perception of asthma is poorly understood and may involve several neurological factors related to disease severity [20-22].

Few studies have used resting state functional magnetic resonance imaging (RS-fMRI) to assess the underlying neurological activities associated with symptom perception. fMRI uses a blood oxygenation level dependent (BOLD) signal to measure and track physiological changes in blood flow and oxygen metabolism in the brain [23]. In addition to BOLD signaling, Diffusion Tensor Imaging (DTI), another mechanism of fMRI, is implemented to track neural pathways and measure anatomical connections between brain areas [24]. This data can be used to identify brain biomarkers and alterations associated with asthma control and the under-perception of dyspnea sensation.

#### 2. OBJECTIVES OF STUDY

- Acquire Xe MRI and optimize analysis methods to generate *in vivo* measurements
- Evaluate Xe MRI measurements over time and in response to therapy, relate them to airflow, dyspnea, airway remodeling and inflammation and validate using x-ray computed tomography (CT) and histology
- Evaluate image analysis methods that generate Xe MRI temporal lung function maps as image guidance/therapy planning tools for targeted asthma therapy
- Develop Xe MRI structure-function models computationally to understand mechanisms of localized therapy response
- Evaluate oscillometry outcomes of the respiratory system as they correlate to lung function abnormalities detected using Xe MRI
- For the subset of patients identified as underperceivers using asthma control and quality of life questionnaires, we will acquire fMRI to determine if severe asthmatics with poor control exhibit baseline differences in brain structure and function compared to healthy volunteers, and if these alterations influence asthma symptom perception.
- To determine if differences in brain structure and function are related to lung function abnormalities quantified by pulmonary MRI
- In healthy volunteers and the subset of asthmatic participants identified as underperceivers, to determine if differences exist in resting state brain connectivity pre- and post-Methacholine challenge
- In the subset of asthmatic participants, to evaluate the differences in resting state brain connectivity compared to healthy volunteers post-Methacholine Challenge

#### 3. HYPOTHESES

- Asthma lung functional abnormalities can be quantified using 129Xe MRI over 2 years correlate significantly and strongly with dyspnea, pulmonary function and sputum measurements as well as indices of asthma quality of life and control. In addition, MRI VDP measured annually over a decade reflects significantly worse remodeling or will improve in response to therapy in those participants who opt for an annual visit.
- Xe MRI ventilation abnormalities are related to airway morphologies due to bronchospasm, airway structural remodeling and inflammation and these can be validated using CT and histology measurements of endobronchial biopsy samples;
- 129Xe MRI temporal functional maps will show significant correlations with functional images acquired 1 year later.
- Asthma underperceivers with poor control will exhibit significant baseline differences in fMRI BOLD contrast and DTI signal data compared to healthy volunteers.

DATE: November 15, 2024

- Quantitative fMRI data will be significantly correlated to pulmonary MRI data that quantifies abnormalities in lung function.
- Healthy volunteers and asthma underperceivers will show significant differences in BOLD contrast after undertaking a Methacholine challenge
- BOLD contrast will be significantly different between asthmatics and healthy volunteers post Methacholine challenge

#### 4. EXPERIMENTAL DESIGN AND METHODS

# 4.1. Overall Design and Control Methods

In 200 asthma patients, we propose to apply Xe MR image acquisition and analysis methods in order to characterize and probe the relationship between lung structure and function using imaging.

The first 60 participants with asthma will also be asked to complete additional follow up visits at the clinic after 2, 4 and 78 weeks. These visits are detailed in the schedule below.

The 30 healthy volunteers will be asked to complete the same study procedures to allow for a comparison between the resting state brain activity as well as lung structure and function between those with and without asthma.

All participants will visit Robarts Research Institute according to the following schedule:

V1 Baseline	V1a* BL+14±2d	V1b* BL+28±2d	V2 Telephone/ optional In-person BL+52±2wk	V1c* BL+78±8wk	V3 Telephone/ optional In-person BL+104±8wk	V4-10 optional in- person annual visit
 Xe/  He MRI	 Xe/  He MRI	 Xe/  He MRI	 Xe/  He MRI	 Xe/  He MRI	 Xe/  He MRI	 Xe/  He MRI
Full PFT	Full PFT	Full PFT	Full PFT	Full PFT	Full PFT	Full PFT
MCh	Meds/Exac	Meds/Exac	Meds/Exac	Meds/Exac	Meds/Exac	Meds/Exac
FOT	FOT	FOT	FOT	FOT	FOT	FOT
FeNO	FeNO	FeNO	FeNO	FeNO	FeNO	FeNO
BORG	BORG	BORG	BORG	BORG	BORG	BORG
MRC	MRC	MRC	MRC	MRC	MRC	MRC
sputum			sputum	sputum	sputum	sputum
СТ						
RS-fMRI (if applicable)						

\*Applicable to only the first 60 participants with asthma.

DATE: November 15, 2024

All participants with asthma will also complete bi-weekly and weekly quality of life questionnaires. Self-reported data will be uploaded by each participant monthly to our website using a confidential and password protected upload.

# 4.1.1. Methacholine Challenge

Methacholine Challenge will be performed for healthy volunteers and asthmatic participants in the Robarts Pulmonary Function Laboratory according to the American Thoracic Society Guidelines (ATS). After recording baseline FEV1, participants will inhale Methacholine solutions up to and including the concentration of Methacholine required to decrease FEV1 by 20% from baseline (PC20). After completion of dyspnea score and He or Xe at PC20, 400 μg of Salbutamol (4 puffs) will be administered followed by spirometry 20 minutes post-administration. Methacholine challenge will be performed at V1 baseline only.

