#### 4.1.2. MRI

Participants will be screened for contraindications by the MR technologist. Prior to being made comfortable on the scanner bed in the magnet, participants will be required to do a 16-second breath-hold test using a dose bag containing air similar to that used for xenon imaging. This maneuver ascertains their ability at that time to undergo administration of Xe gas and a 16-second breath-hold for the MR study. They will be placed in the 3T MR scanner with one of three Xe chest coils fitted over their torso and chest. Hearing protection will be provided to each participant to muffle the noise produced by the gradient RF coils. A pulse oximeter lead will be attached to all of the participants to monitor their heart rate and oxygen saturation. MRI will be performed for up to a period of 30 minutes. All participants will have supplemental oxygen provided via nasal cannula at a flow-rate of 2 liters per minute during the scanning process.

Once comfortable on the MRI scanner table, participants will undergo 1 MRI session containing acquisition of several images as follows:

Proton (H) imaging – participants will inhale a 1 litre gas mixture containing medical grade nitrogen (N2). This is performed in order to match breath hold volumes and anatomy with Xe images. Breath hold will be up to 16 seconds.

Static ventilation imaging – participants will inhale a 1 litre gas mixture containing Xe and or He (5 ml/kg body weight) mixed with helium-4 (He) from a 1 litre bag. Breathhold will be up to 16 seconds.

Diffusion-weighted imaging – participants will inhale a 1 litre gas mixture containing Xe and or He (5 ml/kg body weight) mixed with He from a 1 litre bag. Breath-hold will be up to 16 seconds.

Dissolved phase imaging – participants will inhale a 1 litre gas mixture containing Xe mixed with He from a 1 litre bag. Breath-hold will be up to 16 seconds.

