Logs and records of Xe and He gas exposure will be maintained for every participant in this study. Adverse experiences and pulse oximetry measurements during MRI will be recorded. If oxygen saturation falls to <80% continuously for ≥15 seconds, scanning will be discontinued, and the patient will be provided supplemental oxygen as necessary until oxygen saturation recovers to the patient's baseline value. This patient will then be discontinued from the study.

Participants undergoing resting state fMRI (healthy volunteers and the subset of asthmatic participants identified as underperceivers) will also be placed in the 3T MR scanner with a 32-channel brain coil fitted around their head. Hearing protection will be provided to each participant to muffle the noise produced by the gradient RF coils. A pulse

Protocol ROB0037, Robarts Research Institute Version 16

DATE: November 15, 2024

oximeter lead will be attached to all of the participants to monitor their heart rate and oxygen saturation. MRI will be performed for up to a period of 20 minutes. All participants will have supplemental oxygen provided via nasal cannula at a flow-rate of 2 liters per minute during the scanning process. Participants will undergo fMRI on two occasions during the first visit, each containing acquisition of an anatomical image, a BOLD signal image, and a diffusion tensor image. The sessions will be performed before and after the methacholine challenge for baseline and induced asthma attack or dyspnea conditions, respectively. Outlined in the table below are the appropriate pulse sequences designed for resting state fMR image acquisition:

Brain fMRI and lung MRI using Xe and/or He will be performed within five minutes of each other at both baseline and post-methacholine, and the order in which they are performed will be randomized for each participant and remain the same for both time points.

# Protocol ROB0037, Robarts Research Institute Version 16

DATE: November 15, 2024

MRI RSfMRI Protocol 1 - GE MR 750 Discovery (3T)													
Coil Selection: 32 Channel Head Coil  1. 3 Plane Localizer (2D FGRE)													
TR (ms)	TE (ms)	TI (ms)	FLIP ANGLE	FOV (cm)	FREQ MATRIX (mm)	PHASE MATRIX (mm)	SLICE THICKNESS (mm)	SLICE GAP (mm)	NEX	BANDWIDTH (kHz)	FREQ DIRECTION	ASSET	0:08
5	1.4	N/A	30	24	256	128	10	0	1	31.2	Unswap	N/A	
2. Calibr	ation Sca	ın (3D FS	PGR)										
													0:06
3. Sagitta	al T1 (3D	IR-FSPC	GR)										

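### The salbutamol timing rule in Section 4.1.1 leaves out brain fMRI, so with randomised scan order some lung-first participants could be dosed before the scan meant to image the induced attack

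*Protocol*

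**What the plan says.** Protocol Section 4.1.1 sets the trigger for the bronchodilator. It begins "After completion of dyspnea score and" and then names the 3He or 129Xe acquisition at PC20. After that, 400 μg "of Salbutamol (4 puffs) will be administered followed by spirometry 20 minutes post-administration". Brain fMRI does not appear in the section.

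Section 4.1.2 deals with fMRI, which is for healthy volunteers and the asthma participants identified as underperceivers. On purpose: "The sessions will be performed before and after the methacholine challenge for baseline and induced asthma attack or dyspnea conditions, respectively". On sequence, brain and lung MRI are to be within five minutes of each other at both time points, and "the order in which they are performed will be randomized for each participant and remain the same for both time points".

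No other text holds the dose for the brain scan. The synopsis paragraph on the challenge reads "Methacholine Challenge and Salbutamol rescue: Methacholine Challenge will be performed in the Robarts Pulmonary Function Laboratory at Visit 1" and adds nothing on timing. The synopsis MRI paragraph and Section 8 place fMRI only before and after methacholine. The one mention of salbutamol in Section 8 concerns regional VDP.

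**The concern.** The dosing rule and the purpose of the second fMRI session sit in different sections and do not refer to each other. Under the randomised order, some fMRI participants have the lung scan first. Once that scan and the dyspnea score are done, they have met every condition in 4.1.1 for salbutamol, with the brain scan still to come. A brain-first participant cannot meet the conditions until the brain scan is over.

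If site staff followed 4.1.1 as it stands, the post-methacholine brain data would mix scans taken under bronchoconstriction with scans taken after a bronchodilator, and the mix would follow scan order. Two Section 8 analyses use those data: the paired before/after t-test within each group, and the unpaired t-test of asthma against healthy volunteers after methacholine. The latter serves the hypothesis "BOLD contrast will be significantly different between asthmatics and healthy volunteers post Methacholine challenge". Any correlation of post-challenge fMRI with post-challenge lung MRI would also pair a lung image from before the dose with a brain image from after it. No analysis can restore a provoked state that has already been treated.

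**Working it through.** **Inputs**

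- Trigger for salbutamol: dyspnea score and gas MRI at PC20 (Section 4.1.1).
- Next timed step: spirometry 20 minutes after the dose (Section 4.1.1).
- Lung MRI: "MRI will be performed for up to a period of 30 minutes" (Section 4.1.2).
- Gap between lung and brain scans: 0 to 5 minutes (Section 4.1.2).
- fMRI sequence times (table in Section 4.1.2): localizer 0:08, calibration 0:06, T1 4:38, BOLD 6:00, DTI 8:48.

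**Step 1. Reproduce the stated session length.** 0:08 + 0:06 + 4:38 + 6:00 + 8:48 = 19:40, which matches the table total.

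**Step 2. Lung-first, salbutamol given as the lung scan ends.** Time before BOLD starts within the session is 0:08 + 0:06 + 4:38 = 4:52. BOLD ends at 4:52 + 6:00 = 10:52, and DTI ends at 10:52 + 8:48 = 19:40. Adding the gap between dose and start of the fMRI session:

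| Gap | BOLD, time after dose | End of DTI, time after dose |
|---|---|---|
| 0:00 | 4:52 to 10:52 | 19:40 |
| 5:00 | 9:52 to 15:52 | 24:40 |

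All BOLD data would therefore be collected between 4:52 and 15:52 after the dose.

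**Step 3. Brain-first.** The brain scan precedes the lung scan, and 4.1.1 places salbutamol after the lung scan. No brain image can follow the dose.

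**Step 4. Compare with the 20-minute spirometry.** In the lung-first case of step 2, the session ends before 20:00 only if the gap is under 20:00 − 19:40 = 0:20. Any longer gap overruns the spirometry time. Dosing after both scans has no such clash.

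**Step 5. Wait for salbutamol if it follows both scans.** Lung-first: 30:00 + 5:00 + 19:40 = 54:40 at most from the start of imaging, against 30:00 if dosed straight after the lung scan, so at most 24:40 longer. Brain-first: 19:40 + 5:00 + 30:00 = 54:40, which the protocol already allows.

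**Step 6. Size of any effect on the fMRI results.** This would need the allocation ratio for scan order, the share of fMRI participants reaching PC20, the number of underperceivers, an effect size, and how far and how fast salbutamol reverses the BOLD or DTI signal. The protocol states none of these, so no power loss or bias can be computed from it.

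**The case against.** The strongest reply is that the two sections, read together, already imply the right order. Section 4.1.1 is a general rule for everyone, and being after completion of a step sets an earliest time, not an instruction to dose at once. Section 4.1.2 then says what the second brain scan is for, and a scan under a treated attack would not serve that purpose. The harmful sequence also sits badly with 4.1.1 itself: step 4 shows that it all but rules out spirometry at 20 minutes, since 20 seconds is not enough to give four puffs and change from chest coil to head coil. Dosing after both scans satisfies every sentence.

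Most of this stands. The intended order is probably salbutamol last. But it has to be inferred from a statement of purpose in another section, while the only sentence that times the drug gives a shorter list of conditions. For a participant in bronchoconstriction, early relief is a natural default, and it complies with the text. Nor can this be left to a statistical analysis plan, which does not decide when a drug is given.

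A reader might infer that the protocol orders salbutamol before the brain scan in all lung-first participants, or that half of the fMRI data are spoiled. The documents support neither: dosing after both scans is permitted, and no allocation ratio is stated. A reader might also fault the randomised order. It is sound; the gap is in the dosing rule.

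**Conclusion.** The point holds as a mismatch between the dosing trigger in 4.1.1 and the purpose of the scan in 4.1.2. It is minor. If staff dose after both scans, the loss is zero. If they dose lung-first participants straight after the gas scan, those participants' post-methacholine brain scans are taken after a bronchodilator, with BOLD at 4:52 to 15:52 after the dose. That window assumes dosing as the lung scan ends and an fMRI session starting 0 to 5 minutes later. It does not show that the challenge state would be fully reversed by then.

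It is tempting to attach a loss of power. Any such figure would come wholly from assumed inputs, so none is given. Exposure is confined to post-methacholine fMRI in one part of an exploratory study. The baseline hypothesis, "Asthma underperceivers with poor control will exhibit significant baseline differences in fMRI BOLD contrast and DTI signal data compared to healthy volunteers", and the lung MRI objectives are not affected.

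**What to change.** Amend Section 4.1.1 to say that, in participants undergoing fMRI, salbutamol is given after the dyspnea score and both post-methacholine scans, unless the investigator judges that earlier rescue is needed. Record the clock times of PC20, salbutamol and each scan. Flag any brain scan taken after salbutamol, and report the post-methacholine comparisons with and without those scans. Adjusting these comparisons for scan order is optional and not needed to close the gap.

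The cost is one sentence and a few time stamps on the source document, with no added scans or participants. The downside is the longer wait for lung-first participants, up to about 25 minutes more and about 55 minutes from the start of imaging. Brain-first participants may already wait that long. The rescue override covers anyone who cannot wait.
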